- A pregnant rat embryo-fetal development study (ZYN2-NC-38) executed during the period of major organogenesis did not affect maintenance of pregnancy or fetal survival, growth.

Zynerba has also conducted a 10-week juvenile rat toxicity study (ZYN2-NC-34) where rats tolerated daily doses of CBD up to 80 mg/kg/day for 10 weeks, administered by SC injection in

sesame oil from post-natal day (PND) 12 to 20 (study Days 1-9) and then by transdermal application of ZYN002 from PND 21 to 81 or 82 (study Days 10-70/71). The only adverse effect was on retinal development:

- Chorioretinal dysplasia was identified at a higher rate in ZYN002 rats (18/298 or 6%) compared to the control group (1/200 rats or 0.5%). The finding was not clearly dose related and was higher than historical background incidence (0.4%). (Tanaka et al. 1993; Hubert et al. 1994; Stein et al. 2017).
- Based on the results of the study, pregnant women or women planning to become pregnant should not receive CBD due to the CBD-related increase in the incidence of chorioretinal dysplasia found in juvenile rats. The chorioretinal dysplasia seen in rats would be irrelevant for human subjects exposed after birth because of species differences in ocular development. Briefly, in humans, the eyelids fuse during the third month of gestation and open during the sixth month of gestation. The human retina is largely morphologically mature at birth. In contrast, in rats the eyelids fuse by pre-natal Day 17 (third trimester) and open at approximately post-natal Day 14; consequently, rats are born with fused eyelids and eyes that are not fully developed. In other words, the CBD-related increase in the incidence of chorioretinal dysplasia in juvenile rats was a consequence of exposure to CBD during a period of choroid and retinal development that occurs prior to birth in humans.

Repeat-dose toxicity studies in rats and minipigs with ZYN002 have revealed no effects on endocrine systems or reproductive organs in either species. Published information suggests that CBD has the potential to affect reproductive function in animals, at least in males, possibly secondary to effects on sex hormone levels (Dalterio et al. 1984; Dalterio and deRoos, 1986).

Published information also suggests that administration of CBD to pregnant mice has the potential to affect development of offspring, at least to males (Dalterio et al. 1984; Dalterio and deRoos 1986).

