| Parent/caregiver Completes Daily Skin Irritation Diary ^j | X | X | X | X | X | X | X | |
| Review Patient Skin Irritation Diary | | X | X | | | X | X | |
| Skin Irritation Exam ^k | | X | X | | | X | X | X |
| Adverse Event Review | X | X | X | | | X | X | X |

Table 5 Footnotes - Period 1:

- a. All patients will have a Week 14 Visit/ET. All patients that do not qualify for Period 2 will have an End of Study Visit at Week 14. AED patients will taper study drug for 1 or 2 weeks after the EOS Visit and return on Week 16 or 17 for final discharge from the study.
- b. For patients that do not qualify for Period 2, Week 14/Visit 4 EOS/ET patients will have both weight and height taken. For patients taking AEDs and returning on Week 16 or 17 to be discharged from the study, a targeted physical examination (heart, lungs, abdomen and extremities) may be performed, if the investigator deems clinically relevant.
- c. Vital signs (including blood pressure, heart rate, respiratory rate, and infrared forehead or oral or tympanic temperature) will be recorded after the patient has been sitting for at least 5 minutes. Vital signs will be assessed at each study visit pre-dose.
- d. One ECG to be collected prior to starting treatment (Screening or Visit 2), provided that ECG is normal or has a finding that is not clinically significant.
- e. A pregnancy test will be completed at Week 6, and Week 14/EOS/ET for all females of childbearing potential. Pregnancy tests can be plasma or urine.
- f. Patients receiving valproate or valproic acid will have a blood sample drawn for plasma level of valproic acid. Where possible, effort should be made to get a trough sample. If not, the AED morning dose may be administered prior to the clinic visit. The time of the prior dose of study drug and valproate/valproic acid, if applicable in addition to the time of each blood sample collection will be recorded. During the Treatment Period valproic acid (for patients receiving valproate or valproic acid) blood samples will be taken at Week 6, and Week 14.
- g. On Day 1 the parent/caregiver will be instructed on how to complete the daily skin irritation diary. Scoring of skin irritation will start the evening of Day 1 through discharge from the study by the parent/caregiver. The site will evaluate the parent/caregiver applying the study treatment at each study visit and provide feedback/additional instruction as applicable.

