| Pregnancy Test ^d | | | X | | | X | |
| CBD/THC PK Blood Sample | | | X | | | | |
| Blood Sample for Valproic Acid ^{e, g} | | | X | | | | |
| ABC-C | X | X | X | | | | |
| CGI-S | X | X | X | | | | |
| CGI-I | X | X | X | | | | |
| ADAMS | X | X | X | | | | |

Table 6: Period 2 Schedule of Assessments – 24-Week Extension Treatment Period, cont'd

| Study Procedures | 24-Week Treatment Period – Visit Schedule | | | Taper Period, If Applicable | | Study Visit Week 40 or Week 41 for AED Patients Tapering Study Drug ^a Visit ^a | Un-scheduled Visit(s) |
|--|---|--------------------------------------|---|--|---------------------------|--|--------------------------|
| | Visit 5 Week 22 (± 3 days) | Visit 6 Week 30 (± 3 days) | Visit 7 Week 38 EOS/ET ^a (± 3 days) | Week 39 (± 3 days) | Week 40 (± 3 days) | | |
| | Study Drug Dosing | | | Tapered 50% each week. No Study Visit | | | |
| C-SSRS | X | X | X | | | X | X |
| Qualitative Caregiver Behavioral Problems/Improvements Survey | X | X | X | | | | |
| Children’s Sleep Habit Questionnaire | | | X | | | | |
| Pediatric Anxiety Rating Scale-Revised | X | X | X | | | | |
| Daily Study Drug Application | X | X | X | X | X | | |
| Parent/caregiver Completes Daily Skin Irritation Diary ^{f, h} | X | X | X | X | X | X | X |
| Review Patient Skin Irritation Diary | X | X | X | | | X | X |
| Skin Irritation Exam ⁱ | | | X | | | X | X |
| Adverse Event Review | X | X | X | | | X | X |

Table 6 Footnotes - Period 2:

- a. Patients who withdraw prior to Period 2 Week 38 will complete the EOS/ET at Week 38. AED patients will taper study drug for 1 or 2 weeks after the EOS Visit and return on Week 40 or 41 for final discharge from the study, unless they are transitioning to receive drug through Special Access.
- b. Patients will have both weight and height taken at EOS/ET. For patients taking AEDs and returning on Week 40 or 41 to be discharged from the study, a targeted physical examination (heart, lungs, abdomen and extremities) may be performed, if the investigator deems clinically relevant.
- c. Vital signs (including blood pressure, heart rate, respiratory rate, and infrared forehead or oral or tympanic temperature) will be recorded after the patient has been sitting for at least 5 minutes. Vital signs will be assessed at each study visit pre-dose.
- d. A pregnancy test will be completed at Week 38/EOS/ET for all females of childbearing potential. Pregnancy tests can be plasma or urine.

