8. SELECTION AND WITHDRAWAL OF PATIENTS

8.1. Patient Inclusion Criteria

Patients must qualify based on meeting all of the inclusion and none of the exclusion criteria to be eligible to enroll.

1. Male or female children and adolescents aged 4 to < 18 years, at the time of Screening.
2. Judged by the Investigator to be in generally good health at Screening based upon the results of a medical history, physical examination, and clinical laboratory test results. Laboratory results outside of the reference range must be documented as not clinically significant by the Investigator.
3. Patients must have a diagnosis of 22qDS confirmed by genetic testing, with or without autistic features.
4. Patients have a CGI-S score of 4 or higher at Screening and Visit 2.
5. Patients must have a severity score on the PARS-R of 10 or higher at Screening and Visit 2.
6. Patients with a history of seizure disorders must currently be receiving treatment with a stable regimen of one or two AEDs, or must be seizure-free for one year if not currently receiving AEDs.
7. If patients are receiving non-pharmacological behavioral and/or dietary interventions, they must be stable for three months prior to Screening.
8. Patients have a body mass index between 12–35 kg / m² (inclusive).
9. Patient has demonstrated stable calcium levels for one year prior to Screening.
10. Females of childbearing potential must have a negative pregnancy test at the Screening Visit and a negative pregnancy test at all designated study visits.
11. Patients and parents/caregivers agree to abide by all study restrictions and comply with all study procedures.
12. Patients and parents/caregivers must be adequately informed of the nature and risks of the study and give written informed consent (and assent if applicable) prior to Screening.
13. Parents/caregiver(s) must provide written consent to assist in study drug administration.
14. In the Investigator's opinion, patients and parents/caregivers are reliable and willing and able to comply with all protocol requirements and procedures.

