8.2. Patient Exclusion Criteria

Any of the following is considered criterion for exclusion:

1. Females who are pregnant, nursing, or planning a pregnancy; females of childbearing potential and male patients with a partner of childbearing potential who are unwilling or unable to use an acceptable method of contraception as outlined below for the duration of therapy and for three months after the last dose of study medication.
 - a. Standard acceptable methods of contraception include abstinence or the use of a highly effective method of contraception, including hormonal contraception, diaphragm, cervical cap, vaginal sponge, condom, vasectomy, or intrauterine device.
2. History of significant allergic condition, significant drug-related hypersensitivity, or allergic reaction to any compound or chemical class related to ZYN002 or its excipients.
3. Exposure to any investigational drug or device ≤ 30 days prior to Screening or at any time during the study.
4. Patient has alanine aminotransferase (ALT), aspartate aminotransferase (AST), or total bilirubin levels ≥ 2 times the upper limit of normal (ULN) or has alkaline phosphatase levels ≥ 3 times the ULN as determined from Screening safety laboratories.
5. Use of cannabis or any THC or CBD-containing product within three months of Screening Visit or during the study.
6. Patient has a positive drug screen for sympathomimetic amines (amphetamines (unless prescribed); benzodiazepines; buprenorphine; cannabinoids; methadone; cocaine (metabolites); and opiates; (excludes barbiturates used as AED medication), including ethanol.
7. Patient is using the following AEDs: clobazam, phenobarbital, ethosuximide, felbamate, carbamazepine, phenytoin, or vigabatrin.
8. Patient is using any strong inhibitor/inducer of CYP3A4 or sensitive substrate for CYP3A4 including but not limited to the following medications: midazolam, oral ketoconazole, fluconazole, nefazadone, rifampin, alfentanil, alfuzosin, amiodarone, cyclosporine, dasatinib, docetaxol, eplerenone, ergotamine, everolimus, fentanyl, halofantrine, irinotecan, lapatinib, levomethadyl, lumefantrine, nilotinib, pimozone, quinidine, ranolazine, sirolimus, tacrolimus, temsirolimus, toremifene, tretinoin, vincristine, vinorelbine, St. John's Wort, and grapefruit juice/products.
9. Patient with diagnosis of known genetic disorder, other than 22qDS (i.e. Prader-Willi Syndrome, Angelman Syndrome, Fragile X Syndrome, Rett Syndrome etc.).

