If a patient reports a worsening of skin irritation after a period of improvement, the Investigator should assess whether the event is indicative of a delayed hypersensitivity reaction. If in the opinion of the Investigator the event is a delayed hypersensitivity reaction, this will be recorded as an AE.

All study drug application site signs/symptoms will be recorded as AEs. The event term should specify "application site disorder - [specify sign or symptom]".

If a patient becomes pregnant during or after exposure to a study drug received in this study, the investigator will immediately discontinue the patient from the study and contact the Sponsor or designee. The investigator will complete the Sponsor's (or designee's) Clinical Pregnancy Notification Form and email it to the Sponsor within two days of learning of the pregnancy. Diligent efforts will be made to determine the outcome for all pregnancy exposures in the clinical study. Information on the status of the mother and the child will be forwarded to the Sponsor.

Generally, follow-up will occur within 6 to 8 weeks following the estimated delivery date. Any premature termination of the pregnancy will be reported. Both maternal and paternal exposure will be collected. For exposure involving the female partner of a male participant, the necessary information must be collected from the participant, while respecting the confidentiality of the partner.

Although pregnancy occurring in a clinical study is not considered to be an AE or SAE, any pregnancy complication or elective termination of a pregnancy for medical reasons will be recorded as an AE or SAE and will be followed as such. All reports of congenital abnormalities/birth defects are SAEs. Spontaneous miscarriages should also be reported and handled as SAEs. Elective abortions without complications should not be handled as AEs.

The date of onset and resolution of the adverse event will be collected.

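### No pregnancy test is scheduled between Week 14 and Week 38, although dosed patients attend the clinic at Weeks 22 and 30

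*Protocol*

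**What the plan says.** - **Period 2 schedule (Protocol Table 6).** The pregnancy-test row is marked at Visit 7 (Week 38) and at the Week 40/41 visit for patients tapering study drug. It is blank at Visit 5 (Week 22), Visit 6 (Week 30) and Unscheduled Visits. Footnote d: "A pregnancy test will be completed at Week 38/EOS/ET for all females of childbearing potential". The Period 2 schedule in SAP Section 4.4 is the same.
- **Period 1 schedule (Protocol Table 5, footnote e).** "A pregnancy test will be completed at Week 6, and Week 14/EOS/ET for all females of childbearing potential". Day 1 has no test; the pre-dose test is at Screening.
- **Text sections.** 7.6.15.2 lists the test at Weeks 6, 14 and 38, and 7.6.15.3 and 7.8 list it at the end-of-study visit. 7.6.18 names Screening, Week 6 and Week 14/EOS/ET. None adds a test between Weeks 14 and 38.
- **Eligibility.** Inclusion criterion 10: "Females of childbearing potential must have a negative pregnancy test at the Screening Visit and a negative pregnancy test at all designated study visits". Exclusion criterion 1 removes girls who will not or cannot "use an acceptable method of contraception as outlined below for the duration of therapy and for three months after the last dose".
- **Risk and action.** Section 5.2 concludes that "pregnant women or women planning to become pregnant should not receive CBD due to the CBD-related increase in the incidence of chorioretinal dysplasia". If a patient becomes pregnant, Section 11.2.1.1 states that "the investigator will immediately discontinue the patient from the study and contact the Sponsor or designee".

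**The concern.** The protocol takes a firm position on pregnancy but gives itself little means of acting on it in the extension. Section 5.2 attributes the juvenile-rat retinal finding to "exposure to CBD during a period of choroid and retinal development that occurs prior to birth in humans", which makes gestation the relevant exposure window. It also cites published work suggesting that "administration of CBD to pregnant mice has the potential to affect development of offspring, at least to males". Stopping the drug at once limits exposure only if the pregnancy is known.

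Inclusion criterion 10 does not fill the gap. It relies on designated visits, and none is designated for 24 weeks. If contraception fails and nobody reports a pregnancy, a girl could dose twice daily through two clinic visits without being tested. The stake is fetal exposure that the protocol says should not happen. Efficacy and safety summaries are unaffected.

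**Working it through.** The documents state no testing interval, so there is no figure of theirs to reproduce. The check is date arithmetic on the visit schedule.

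**Inputs**
- Test visits: Screening, Weeks 6, 14 and 38 (Tables 4, 5 and 6; Section 7.6.15.2).
- Period 2 clinic visits: Weeks 22, 30 and 38, with daily application marked at all three (Table 6).
- Visit window: ±3 days from Week 6 onward (Tables 5 and 6).
- Screening window: Days -28 to -8 (Table 4).
- Dosing: twice daily (Section 7.4).
- Month length: 30.44 days (SAP Section 6.1.1).

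**Present gap, Week 14 to Week 38**
- (38 − 14) × 7 = 168 days; 3 days either way at each end gives 162 to 174 days.
- 168 / 30.44 = 5.52 months (5.32 to 5.72 with the windows).
- 168 × 2 = 336 applications.

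**Comparators in Period 1**
- Week 6 to Week 14: (14 − 6) × 7 = 56 days (50 to 62).
- Screening to Week 6: longest 28 + 42 + 3 = 73 days; shortest 8 + 42 − 3 = 47 days.
- The Period 2 gap is 168 / 56 = 3 times the on-treatment interval of Period 1.

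**With tests at Weeks 22 and 30**
- Each Period 2 interval becomes 8 × 7 = 56 days (50 to 62), or 56 × 2 = 112 applications.
- 56 / 168 = one third of the present gap. The longest gap in the study would then be Screening to Week 6.

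**Girls affected (assumption; the documents give no figure)**
- Suppose 2 to 5 of about 20 patients are girls of childbearing potential, and 25% to 75% of them enter Period 2.
- 2 × 0.25 = 0.5 to 5 × 0.75 = 3.75 girls.
- Two added tests each: 1 to 7.5 tests in total.

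**Could anything else at Weeks 22 and 30 detect a pregnancy?** Table 6 schedules no laboratory tests, urinalysis or physical examination at those visits. Adverse events are reviewed, but Section 11.2.1.1 says that pregnancy is not itself an adverse event. A pregnancy might come up in conversation, but nothing scheduled would find it objectively.

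**The case against.** The strongest reply is that this is a coherent design choice. Weeks 22 and 30 are light visits, pregnancy testing follows the laboratory visits, and the documents set no maximum interval that is breached. The 8-week comparator is simply the Period 1 visit spacing. That is fair: the gap contradicts no stated testing rule. It does sit badly with the protocol's own conclusion on pregnancy, and no reason is given for tripling the interval.

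Other points stand in part:
- **Mitigations.** Contraception or abstinence is required, girls planning pregnancy are excluded, caregivers apply the gel daily, and early leavers should be tested at the termination visit. These lower the risk and make 168 days a maximum. However, several accepted methods (abstinence, condom, diaphragm, cap, sponge) depend on adherence. Self-report is also uncertain in a syndrome where Section 5.1 puts mild to moderate intellectual disability at about 45%.
- **Numbers.** If annual pregnancy incidence were 1% to 5% (an assumption), then over 168 / 365.25 = 0.46 years, 0.5 to 3.75 girls give about 0.002 to 0.09 expected pregnancies. This bears on priority.
- **Harm evidence.** The retinal finding was not clearly dose related, and early dosing in that study was by subcutaneous injection. The sponsor's rabbit study showed no embryo-fetal effect, and its rat study no effect on maintenance of pregnancy or on fetal survival or growth. With these results in hand, the protocol still concludes that pregnant women should not receive CBD.
- **The first gap.** Screening to Week 6 can reach 73 days, and tests at Weeks 22 and 30 leave it untouched. That is correct, but it is less than half of 168 days.

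**Conclusion.** The concern holds. For girls of childbearing potential in Period 2, no test is scheduled for up to 168 days (162 to 174), about 5.5 months of twice-daily dosing, although they attend the clinic twice in that time. The interval follows directly from the schedule and needs no assumption. The number of girls affected, at most about four, does rest on an assumed range.

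The matter should be corrected because the protocol rules out CBD in pregnancy and the remedy is cheap. Its priority is limited by the small numbers, the mixed nonclinical evidence and the contraception requirement. It has no bearing on the validity of the analyses.

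**What to change.** - In Protocol Table 6, mark the pregnancy test at Visit 5 (Week 22) and Visit 6 (Week 30), and extend footnote d to those visits. Urine testing is already permitted. Match the copy in SAP Section 4.4.
- As a wording clean-up, make Section 7.6.18 list Screening, Weeks 6, 14, 22, 30 and 38/EOS/ET, and the taper visit.

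The cost is a protocol amendment, which needs ethics committee approval before it takes effect (Section 16.1), plus two urine tests per eligible girl at visits already attended: about 1 to 8 tests in the whole study under the assumption above. No new type of procedure is needed. The downside is a small extra burden for those girls.

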7.6.2. Informed Consent

Signed informed consent will be obtained at Screening from parent/caregivers and if applicable assent will be obtained from patients where developmentally appropriate. The informed consent form (ICF) will be signed by the parent/caregiver and the assent by the patient (if applicable) before any study procedures are undertaken. Details about how the ICF will be obtained and documented are provided in Section [17.3](#).

7.6.3. 22q.11.2 Deletion Syndrome Diagnosis

Patients participating in this study will have a diagnosis of 22q.11.2 (also referred to as 22qDS) confirmed by genetic testing, with or without autistic features.

7.6.4. Demographics

At the Screening Visit, patient demographic information will be collected and recorded in the CRF.

7.6.5. Vital Signs

Vital sign determinations include sitting blood pressure, heart rate, respiratory rate, and infrared forehead, or oral or tympanic body temperature will be recorded. Vital signs will be recorded after the patient has been sitting for at least 5 minutes. Vital signs will be assessed pre-dose at all study visits.

7.6.6. Medical History

A complete medical history for the previous 5 years will be obtained from each patient during the Screening Visit.

7.6.7. Concomitant Medication Review

Medication (prescription and OTC) use will be recorded at the Screening Visit and updated at Day 1 (prior to dosing). A review of patient concomitant medication will be performed at each study visit, Unscheduled Visits, the Week 10 Telephone Follow-up call, and at the End of Study Visit.

7.6.8. Review Adverse Events

A review of AEs will be performed at Screening, and each study visit, the Week 10 Telephone Follow-up call, and any Unscheduled Visits. Detailed information regarding AEs can be found in Section [11.2](#).

7.6.9. Complete Physical/Neurological Examinations

A complete physical and neurological examination, including height and weight will be performed at Screening and Visit 4/Week14 and Visit 7/Week 38 EOS/ET. Only patient weight will be collected at Visit 4 and Visit 7 EOS/ET. Patient weight will be collected with minimal clothing (e.g., no coats, shoes, jumpers or jackets).

A complete physical and neurological examination will be performed at Day 1, Week 6 and Week 38/EOS/ET.

7.6.10. Targeted Physical Examination

For patients taking AEDs and returning on Week 40 or 41 to be discharged from the study, a targeted physical examination (heart, lungs, abdomen and extremities) may be performed, if the investigator deems clinically relevant.

